### **3.10 Clinical outcome indicators and assessments**

1. Surgical site infection: assessment of the surgical site infection includes the types of infection (deep and superficial), sternal dehiscence, and percentage of the surgical site infection and sternal dehiscence. The participants will be assessed at day 0, at the end of the hospital stay, day 14 post - operative, and day 30 – post operative. All of the sternotomy wound will be documented digitally at day 0, at the end of the hospital stay, day 14 post – operative, and day 30 post-operative.

2. Haemostasis effect: It will assess the quantity of blood lost from the sternal edges in Sternum Guard™ and Bone Wax group. The Sternum Guard™ and sterile drapes will be weighed before and after surgery to estimate the blood lost.
  
3. Satisfaction Rate: The satisfaction rate will be evaluated using a questionnaire distributed to the surgeons. The questionnaire will contain overall satisfaction, ease of placement, maintenance of a dry field throughout the surgery, ease of removal; each of this question will have four different response which are satisfied, fairly satisfied, fairly dissatisfied, dissatisfied. Additionally, the surgeons will be asked about the experience in using Sternum Guard™ as compared to Bone Wax and it will contain 3 different response: worse, similar, better.

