with modified cellulose designed specifically to reduce the risk of surgical site infection. It is a sternal protection device that covers the sternum after median sternotomy and has specific mechanical protection that prevents lesions on the sternum. It is made from a non-woven material. Sternum Guard™ provides haemostatic effect through a natural reaction to compression and blood absorption. Moreover, it decreased the bacterial proliferation by decreasing the pH. The Sternum Guard™ covers the entire incision angle and subcutaneous tissue and it has very low particle release. It is easy to use and maintains a dry surgical site. 

However, there are still insufficient evidence to support the use of modified cellulose non-woven material in cardiac surgery. Thus, in this study we would like to compare the efficacy of Sternum Guard™ as opposed to Bone wax in post cardiac surgery patients.

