### **3.6 Data extraction**

Every participant included in this study will be scheduled for any cardiac surgery electively. Every participant will undergo the surgery with cardiopulmonary bypass. All of the surgery will be conducted in a similar manner, however, if there is any complication intraoperatively, every action will be taken according to the situation and will be recorded. Before incision the Sternum Guard™ and sterile drapes for the bone wax group will be weighed. After median sternotomy, the surgeons will be given Bone Wax or Sternum Guard™ to be applied to the sternum. The decisions will be made based on the block randomisation technique and will be informed beforehand to the nurse scrub and the surgeon. In the Bone Wax group, cauterization will be used according to the sternum's condition and surgeon's decision before applying the sterile draping and after removing it if needed. In the Sternum Guard™ group, cauterization will also be applied before inserting it to the sternum and after removing the Sternum Guard™ if needed.

Subsequent to median sternotomy, sternal bleeding will be assessed. In the Sternum Guard™ group, immediately before cauterization and in Bone Wax group right before applying the bone wax.

Once the surgery is done, the Sternum Guard™ and the sterile drapes will be weighed again. Sternal trauma will be evaluated at the end of surgery (visible trauma or no visible trauma). In the Sternum Guard™ group, within 5 minutes of Sternum Guard and sternal retractors removal and on the Bone Wax group within 5 minutes of removal of the sterile drapes and sternal retractors. Another sternal bleeding assessment will be done on both groups. In the Sternum Guard™ group it will be assessed immediately after removing the Sternum Guard, before the cauterization, while on the Bone Wax group, before applying any bone wax and cauterization. The sternotomy wound will be evaluated and documented at Day 0, at the end of hospital stay, Day 14 post - operative, and Day 30 post-operative. After the surgery, the surgeons will be given questionnaire regarding the use of Sternum Guard™ as opposed to Bone Wax.

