#### B. Treatment Group with Sternum Guard™:

Group of patients who undergo cardiac surgery with the use of cardiopulmonary bypass and use Sternum Guard™ to protect the sternum after median sternotomy.

Table 1 - Table of Operational Definition

	Variable	Definition	Type of Data	Code
1	Age	The age of participant when undergo the cardiac surgery, it defines with calculated birth year taken from the medical record	Numerik	
2	Gender	Gender which is included in this study are based one the	Categorical	1 = Male 2 = Female

		data recorded in the medical record.		
3	Comorbid	Data extracted from anamnesis and the medical record, with blood pressure $\geq 140/90$ mmHg and diabetes mellitus (Fasting Blood Glucose $>126$ mg/dL or 2 hr post prandial blood glucose or one time blood glucose $>200$ mg/dL)	Categorical	1 = Yes 2 = No
6	Cardiac Surgery	Any cardiac surgery that are conducted in adult cardiac surgery division which are using cardiopulmonary bypass	Categorical	1 = CABG 2 = Valve 3 = CABG + Valve 4 = Vascular
7	Surgical Site Infection	Surgical site infection is divided by 2 categories (Superficial: infection occurs just in the area where the incision is made; Deep: occurs beneath the incision area in muscle and the tissues surrounding the muscle). It is evaluated at day 0, at the end of hospital stay, day 14 post – operative and day 30 post-operative	Categorical	1 = Deep 2 = Superficial
8	Sternal Dehiscence	Occurs when there is an evidence of sternum separation. Often	Categorical	1 = Yes 2 = No

[figure not shown]
		accompanies with mediastinitis.		
9	Haemostasis Effect	The data obtained by quantity of blood lost from the sternal edges in Sternum Guard TM and Bone Wax group. The Sternum Guard TM and sterile drapes will be weighed digitally before and after surgery to estimate the blood lost.	Numeric	
10	Satisfaction Rate	The result obtained by the questionnaire in both groups.  Overall satisfaction rate  Maintenance of a dry surgical field during intervention (both groups)  Haemostatic effect  Ease of insertion (Sternum Guard TM group)  Ease of removal (Sternum Guard TM group)	Categorical	1 = Satisfied 2 = fairly satisfied 3 = fairly dissatisfied 4 = dissatisfied
12	Experience satisfaction rate	The result obtained by the questionnaire for the Sternum Guard TM group.	Categorical	1 = worse 2 = similar 3 = better

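### Haemostasis is scored as the weight gained by two different coverings that are not shown to capture blood equally, so a between-arm difference in grams may reflect the coverings as well as the bleeding

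*Combined protocol and SAP*

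**What the plan says.** Section 3.10, item 2, defines the haemostasis effect by weight: "The Sternum Guard™ and sterile drapes will be weighed before and after surgery to estimate the blood lost". Table 1, row 9 (section 3.11) gives the same definition, beginning "The data obtained by quantity of blood lost from the sternal edges in Sternum Guard" and going on to name the bone wax group. Section 3.6 shows which object belongs to which arm: "Before incision the Sternum Guard™ and sterile drapes for the bone wax group will be weighed". Table 3 reports the result in grams per arm, in a row below the heading for primary outcomes. Section 3.9 would compare a numerical variable of this kind by t-test or Mann-Whitney test.

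On the device, section 1.1 says: "Sternum Guard™ provides haemostatic effect through a natural reaction to compression and blood absorption". No absorbency is stated for the drapes.

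Section 3.6 also schedules two direct looks at the sternum. The first: "Subsequent to median sternotomy, sternal bleeding will be assessed", timed in the Sternum Guard arm "immediately before cauterization and in Bone Wax group right before applying the bone wax". The second comes at the end of surgery: "Another sternal bleeding assessment will be done on both groups". No bleeding scale is given for either.

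Objective 3 in section 1.5 counts mechanical protection among the aspects of surgeon satisfaction to be compared.

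**The concern.** Objective 2 is a head-to-head comparison of haemostasis. Apart from ratings by surgeons who know the allocation, grams are its only named measure. The quantity wanted is bleeding from the cut bone. The quantity recorded is the fluid that stays in whatever was laid over it, and that object differs by arm. In one arm it is the treatment itself, so absorption that section 1.1 counts as part of the haemostatic action also adds to the weight counted as blood lost.

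If the coverings differ in what they catch and keep, the planned test could report that difference as a haemostasis effect, or could hide a real one. The plan has no comparability check, conversion or correction for other fluid, and no caveat on how the grams should be read.

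The questionnaire gap is separate and smaller: one stated part of objective 3 has no data source.

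**Working it through.** **The plan's own figures.** The plan gives no SD, target difference or power for grams. Its only size calculation (section 3.7) is for two proportions, 0.15 and 0.05, two-sided 5%, power 90%. With a mean proportion of 0.10:

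n = {1.960·√(2·0.10·0.90) + 1.282·√(0.15·0.85 + 0.05·0.95)}² / 0.10² = (0.832 + 0.536)² / 0.01 ≈ 187.1, so 188 per arm and 376 in total, as stated.

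376 × 1.10 = 413.6, giving 414, or 207 per arm; Table 6 lists 207 devices. These figures reproduce but say nothing about the weighing.

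**Time in place.** Both coverings go on after sternotomy. Section 3.6 times the trauma check from removal of the covering and retractors in each arm; for bone wax it reads "on the Bone Wax group within 5 minutes of removal of the sterile drapes and sternal retractors". The periods look broadly similar, so the issue is capture rather than duration.

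**What the grams contain.** Let μ be mean sternal blood loss, f the share that ends up in the weighed covering, and x any other fluid it holds (S = Sternum Guard, D = drapes). The expected difference in weight gain is

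Δ = f_S·μ_S − f_D·μ_D + (x_S − x_D).

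With f_S = f_D and x_S = x_D, Δ keeps the sign of the true difference. Otherwise it need not. The documents give no value for any f or x.

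**Illustration only.** The capture shares are assumed, x is set equal in both arms, and μ_D = 1:

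- Equal bleeding, capture 0.9 v 0.8: Δ = 0.9 − 0.8 = +0.10. With the shares swapped: −0.10.
- Sternum Guard truly 20% lower, equal capture 0.8: Δ = 0.64 − 0.80 = −0.16 (sign correct).
- Sternum Guard truly 20% lower, capture 0.9 v 0.72: Δ = 0.72 − 0.72 = 0 (effect hidden).
- Sternum Guard truly 20% lower, capture 0.9 v 0.6: Δ = 0.72 − 0.60 = +0.12 (sign reversed).

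For equal bleeding, the chance of p < 0.05 at 188 per arm uses SE = CV·√((f_S² + f_D²)/188) and P = 1 − Φ(1.96 − Δ/SE) + Φ(−1.96 − Δ/SE). At 0.9 v 0.8 and CV 0.5, SE = 0.0439 and Δ/SE = 2.28.

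| Capture (S v D) | CV 0.5 | CV 0.75 | CV 1.0 |
|---|---|---|---|
| 0.8 v 0.8 | 0.05 | 0.05 | 0.05 |
| 0.9 v 0.8 | 0.625 | 0.330 | 0.207 |
| 0.9 v 0.7 | 0.998 | 0.894 | 0.672 |

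The range is wide and rests wholly on assumed values. It shows that the mechanism matters if capture differs, not how large the distortion is in this trial.

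**The bleeding checks.** At the first check neither product has been applied: it precedes the wax in one arm, and in the other it precedes the cautery that comes before the guard is inserted. It is a baseline reading. At the second check both arms are read before cautery. The Sternum Guard arm is read immediately after the device comes off, while the bone wax arm is only required to be read before any wax or cautery.

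**Questionnaires.** Both forms cover overall satisfaction, placement, dry field, haemostasis and removal. The list in section 3.10 covers overall satisfaction, placement, dry field and removal. Mechanical protection appears in none of them.

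**The case against.** The strongest reply is that if nearly all sternal-edge blood ends up in whichever covering is used, weight gain tracks blood lost whatever the absorbency. Bias arises only if the coverings take up different shares of blood or other fluid, and the documents do not say that they do. This stands. A reader might infer that the grams cannot measure blood loss at all, or that they must count against Sternum Guard because it absorbs. Neither is supported: comparability has not been shown, but nor has it been disproved.

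A reader might also gauge the problem by t-test sensitivity. At 188 per arm an observed difference of about 0.20 SD reaches p < 0.05. That is true of any numerical outcome in a trial of this size and does not measure this distortion.

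It is also tempting to say that the bleeding checks would go unanalysed, or that they should replace the weighing. Section 3.9 covers all collected data, and the general haemostasis term in 1.5 and 3.8 could include them. The row numbers of Table 1 skip in the text available, so nothing is claimed about its omissions. As a replacement, an ungraded visual reading at one moment, possibly by someone who knows the allocation, is not clearly better than a digital weight. Leaving a baseline reading off the outcome list is no defect.

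**Conclusion.** The point holds as a limit on interpretation. The arms weigh different objects, the text shows no equivalence between them, and the plan would still read the difference as blood lost. Its size and direction are unknown. It should be corrected because haemostasis is a stated objective, its row sits under the primary-outcome heading in Table 3, and the correction is nearly free.

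The reach is objective 2 only. The hypothesis in 1.4 concerns infection and dehiscence, and the calculation in 3.7 is for proportions; neither is touched. The conclusion assumes that no comparability check is described outside the text available, which lacks the research-flow figure.

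The questionnaire gap also holds: the mechanical-protection part of objective 3 cannot be answered with the forms as written.

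**What to change.** - In 3.10, Table 1 row 9 and Table 3, keep the weighing but label it as weight gained by the covering (g). State that no difference in blood loss or haemostasis will be concluded from it alone.
- Report the end-of-surgery sternal bleeding check by arm beside the weights, as supporting evidence and not as a substitute. Fix a simple grade in advance, use the same timing after removal of the covering in both arms, and note that the scorer may be unblinded.
- Describe the first bleeding check as a baseline reading.
- Add one mechanical-protection item to both questionnaires and to the list in 3.10.

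The cost is text edits, one defined grade and one extra item per form. No visit or procedure is added, because the check is already scheduled. The downside is that objective 2 will support a more cautious conclusion.

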**Specific Objectives:**

1. To compare the surgical site infection and sternal dehiscence rates at the end of hospital stay, day 14 post operation, and day 30 post operation in post cardiac surgery patient with the application of Sternum Guard™ as opposed to bone wax intraoperatively.
2. To compare the haemostasis effect of Sternum Guard™ as opposed to bone wax intraoperatively in cardiac surgery.
3. To compare the satisfaction rate (includes global satisfaction rate, haemostasis and dryness of surgical site, and mechanical protection) of the surgeons who are using the Sternum Guard™ as opposed to bone wax intraoperatively in cardiac surgery.

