### 3.7 Sample size estimation

The sample size in this study is estimated by using the formula for hypothesis tests for two population proportions (two-sided test)

$$n = \frac{\left\{ Z_{1-\alpha/2} \sqrt{2\bar{P}(1-\bar{P})} + Z_{1-\beta} \sqrt{P_1(1-P_1) + P_2(1-P_2)} \right\}^2}{(P_1 - P_2)^2}$$

details:

$\alpha$  : 5

$1-\beta$  : 90

$P_1$  : 0.15

$P_2$  : 0.05

$n$  : 376

From the equation above, it is estimated for the sample size of the study to be 376 samples, with estimated drop out proportion of 10%, it is deduced the sample size of 414 samples.

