### **3.9 Data analysis**

All collected data will be verified and will be statistically analyzed using SPSS and the result from the data analysis was considered statistically significant with a p-value of  $< 0.05$ . For descriptive analysis, we will perform the analysis independently for numerical and categorical data. All numerical data will be analyzed using Coefficient of Variance and confirmed by Kolmogorov-Smirnov normality test. Normally distributed data will be analyzed using mean and standard deviation, meanwhile the abnormally distributed data will be analyzed using median, minimum value and maximum value. Categorical data analysis will be presented by percentage and frequencies table.

For inferential data analysis, we will perform the comparison tests and mean comparison test. The proportion comparison tests are applied for comparing categorical independence variable between Sternum Guard™ and bone wax group, such as Chi-square test and Fisher's Exact test as an alternative for chi-squared test. Mean comparison tests are utilized for comparing numerical independence variable between Sternum Guard™ and bone wax group, such as Independent T-Test and Mann-Whitney test for the non-parametric test.

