#### Outcomes

Table 3 - Dummy Table 2

	Sternum Guard™		Bone Wax	
	N	%	N	%
Primary Outcomes				
Surgical Site Infection:				
Superficial *				
Deep *				
Sternal Dehiscence:				
Yes *				
No *				
Haemostasis Effect (gr)**				
Satisfaction Rates **				
Satisfied				
Fairly satisfied				
Fairly dissatisfied				
Dissatisfied				

\*) n(%)

\*\* ) mean + SD

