## Questionnaire for the Surgeons

**Efficacy of Sternum Guard™ in comparison of Bone Wax in Post Cardiac Surgery**

**Patient: A Single Blind, Single Centre, Randomized Control Trial**

Research Principles: dr. [name], B.MedSc. ; Dr. dr. [name], Sp. BTKV (K) MARS.

Section 1 (Bone Wax)	Surgeon's Satisfaction with Bone Wax				Comments
	Satisfied	Fairly Satisfied	Fairly Dissatisfied	Dissatisfied	
Overall Satisfaction					
Ease of placement					
Maintenance of a dry field throughout the surgery					
Haemostasis effect					
Ease of removal (if any)					

Comment (s):

1.

Time and Date:  
Investigator:

Group:  
Patient's initial:

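### Objective 3 rests on three to five satisfaction items with no key item named; if each is tested at 5%, the chance of at least one false positive is about 10–23%

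*Combined protocol and SAP*

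**What the plan says.** Five places describe the satisfaction outcome, and they do not agree.

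- **Section 1.5, specific objective 3:** "To compare the satisfaction rate (includes global satisfaction rate, haemostasis and dryness of surgical site, and mechanical protection) of the surgeons". This is one rate with several named components.
- **Section 3.10, item 3:** "The questionnaire will contain overall satisfaction, ease of placement, maintenance of a dry field throughout the surgery, ease of removal". Four items; haemostasis is not among them.
- **Section 3.11, Table 1, row 10:** five items, classed as categorical. Insertion and removal are limited to the Sternum Guard group. Dry field is marked for both groups. Overall satisfaction and haemostatic effect carry no group label.
- **Questionnaires (Appendix):** the same five four-level items in both arms, namely overall, placement, dry field, haemostasis and removal. The bone wax form qualifies the last as "Ease of removal (if any").
- **Section 3.14, Table 3:** a single block headed "Satisfaction Rates", with four response rows, under the heading for primary outcomes. No item is named. Its footnote marker calls for mean and SD.

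Mechanical protection, named in Objective 3, is on neither form.

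On testing, section 3.9 says results are "considered statistically significant with a p-value of" less than 0.05, and assigns chi-square or Fisher's exact tests to categorical variables. It gives no key satisfaction item, composite score, hierarchy or multiplicity adjustment. Section 3.5 states that the surgeons, who are the raters, know the allocation.

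**The concern.** This is multiplicity inside one outcome. It is separate from the choice among infection, dehiscence, haemostasis and satisfaction. Several items feed one objective, each falls under the same 5% rule, and there is one unlabelled place to report the result. An analyst following the text could test every item and put the most favourable one in the Table 3 block without departing from the plan. A satisfaction claim reached that way would not carry a 5% error rate.

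It matters because satisfaction is one of three specific objectives and is listed with the primary outcomes. It is also a subjective rating by unblinded surgeons, so the analysis should leave little room for choice after the data are seen.

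**Working it through.** **Inputs from the documents**
- Threshold 0.05 for all results (section 3.9). The sample-size calculation is two-sided (section 3.7), and Objective 3 is a comparison with no stated direction, so two-sided tests are used.
- Number of items that can be compared between arms, k: three if Table 1's limit on insertion and removal holds (overall, dry field, haemostasis); four if section 3.10 is followed; five if the two forms are followed.
- Size: section 3.7 gives 376. Its formula with 0.15, 0.05, two-sided 5% and 90% power gives 187.05, rounded up to 188 per arm, and 2 × 188 = 376. So the figure reproduces. With the 10% allowance, 376 × 1.1 = 413.6, rounded to 414, or 207 per arm, which matches the 207 devices in Table 6. These sizes are needed only for the simulation below.

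**Assumptions, not in the documents**
- A common correlation ρ between the item test statistics, shown from 0 to 0.8.
- Ratings are independent.
- Every item is tested, and any one significant item is taken as the result.

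**Formulas**
- One pre-named item: 1 − 0.95 = 5%.
- k independent items: 1 − 0.95^k. For k = 3, 1 − 0.8574 = 14.3%. For k = 4, 1 − 0.8145 = 18.5%. For k = 5, 1 − 0.7738 = 22.6%.
- k equally correlated items, with c = 1.96: 1 − ∫ φ(u) [Φ((c − √ρ·u)/√(1−ρ)) − Φ((−c − √ρ·u)/√(1−ρ))]^k du.
- Differences favouring Sternum Guard only: the same integral without the second Φ term. For independent items this is 1 − 0.975^k.

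**Chance of at least one false positive (two-sided / favouring Sternum Guard only)**

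| ρ | 3 items | 4 items | 5 items |
|---|---|---|---|
| 0 | 14.3% / 7.3% | 18.5% / 9.6% | 22.6% / 11.9% |
| 0.3 | 13.6% / 6.8% | 17.4% / 8.7% | 20.9% / 10.5% |
| 0.5 | 12.5% / 6.3% | 15.6% / 7.8% | 18.3% / 9.2% |
| 0.8 | 9.8% / 4.9% | 11.4% / 5.7% | 12.7% / 6.4% |

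The single-item benchmarks are 5% and 2.5%. The smallest entry is therefore 9.8/5 = 1.96 times its benchmark, and the largest is 11.9/2.5 = 4.8 times.

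**Check with the planned chi-square test.** Four-level items were simulated with no true difference, 207 per arm, assumed response shares of 50/30/15/5% and 3,000 trials per setting. At latent correlations of 0.3, 0.5 and 0.7, three items gave 13.6%, 13.3% and 12.2%, and five gave 21.4%, 21.7% and 21.4%. The simulation error is roughly 0.6 to 0.75 percentage points. The results fall inside the two-sided range over ρ for three and for five items.

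**The case against.** The strongest reply is that the plan never says any one item is enough. Objective 3 only asks for a comparison. The hypothesis in section 1.4 covers infection and dehiscence, section 3.7 sizes the trial on one pair of proportions, and Table 3 has no column for p-values. This stands. A reader might infer that the protocol adopts a rule under which the best item wins, with a fixed false-positive rate near 20%. The documents do not support that: item-by-item testing is permitted by silence, and the rate depends on a correlation they do not give.

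Further points also stand, in part or in full:
- **Footnote in Table 3.** Mean and SD could point to one numeric score, which section 3.9 would send to a t-test or Mann-Whitney test. Table 1 makes the variable categorical and no scoring is defined, so the marker adds a conflict and does not settle the analysis.
- **Direction.** If the feared error is a false claim for Sternum Guard, the absolute figure is about half the two-sided one. The relative inflation remains.
- **Comparability.** A reader might infer that neither placement nor removal has a control counterpart. That goes too far for placement: the bone wax form collects it, and ease of applying two products can be compared. Only removal lacks a clear counterpart. Section 2.5 says wax stays on the bone, and if the item refers to the drapes of section 3.6, the form does not say so.
- **Independence.** Forms are completed per patient, the number of surgeons is not given, and section 3.9 does not address repeated ratings. Choosing one item does not by itself guarantee 5%, nor does it remove bias from unblinded raters.

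**Conclusion.** The point holds conditionally. The documents leave three to five satisfaction items under one blanket 5% rule, with one unlabelled reporting slot and conflicting lists of what is compared. If each item is tested and any one is taken as the result, the two-sided chance of a false positive is about 10–14% for three items and 13–23% for five. In favour of Sternum Guard alone it is about 5–12%, against 2.5% for a single item. The ranges rest on assumed correlations from 0.8 down to 0 and on independent ratings. The effect is confined to the satisfaction claim; it does not touch the infection or dehiscence comparison. It is worth correcting because the outcome is listed as primary and wording alone is enough.

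**What to change.** 1. In sections 3.9 and 3.10, name overall satisfaction as the only between-arm test for Objective 3, at two-sided 5%. It appears in every satisfaction list (as the global rate in Objective 3).
2. Label the Table 3 block as overall satisfaction and show it as n (%) in place of mean and SD, in keeping with Table 1.
3. Report dry field, haemostasis and ease of placement by arm as exploratory, without a significance claim. If the sponsor wants claims on the components named in Objective 3, test them with Holm's procedure instead. For overall, dry field and haemostasis the ordered p-values would be compared with 0.05/3 = 0.0167, 0.05/2 = 0.025 and 0.05, which keeps the family-wise rate at or below 5% whatever the correlation.
4. Report ease of removal descriptively.
5. Align Objective 3, section 3.10, Table 1, Table 3 and the two forms to this list, and take mechanical protection out of Objective 3's satisfaction list, since no questionnaire item measures it.

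This needs no extra patients or data. The cost is that, under the single-test option, a difference seen only on a component item becomes exploratory. It does not deal with repeated ratings by the same surgeons, which would need its own sentence in section 3.9.
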